## 10.0 Statistical Considerations

### 10.1 Preliminary Analyses

Premature Termination. Patients will be considered dropouts (a) if they miss two or more sessions or (b) if serious adverse reactions or clinical complications (e.g., suicidal intention) develop. Initial data analyses will be conducted on treatment completers. This will address relative efficacy among treatment completers. A second analysis will be conducted including all patients who initiate treatment using an intent-to-treat analysis. This will address relative efficacy in the population intended for treatment, thus incorporating issues related to potential differential dropouts in the treatment groups. Finally, analyses will be conducted to see if treatment completers differ from drop-outs on demographic variables and pre-treatment measures.

Group Equivalence. We will evaluate the effectiveness of random assignment to two treatment groups by comparing the groups on demographics, baseline measures of key outcome variables, and other important theoretical covariates. We will characterize differences between study dropouts and completers, and between dropouts from the VRE+DEX and VRE+placebo groups. We will compare dropouts to completers on the same set of baseline variables that will be used to examine initial group equivalence. Differences between conditions will be assessed using one way ANOVA for continuous variables and chi-square analyses for categorical variables (Fleiss et al., 2013). Any observed differences that approach statistical significance ( $P \leq 0.15$ ), and which are theoretically or empirically identified as potential confounders will be included as covariates in subsequent cross sectional and longitudinal analyses.

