### 10.2 Statistical Analyses

#### Power and Sample Size

Power calculations are based on Cohen (1992). We set the Type I Error rate at 0.05 (two-tailed) for all computations. We first calculated the number of participants needed to test the effect of VRE augmentation with DEX at immediate post-treatment assessment (Hypothesis 1 above). Then, knowing how many participants would be needed at the end of this phase, we worked backward to calculate how many participants would need to be enrolled initially. We will continue to collect data from all participants, including those who drop out of treatment or are discontinued. Thus, loss to the study represents a failure to participate in measurement, and not merely dropout from treatment. We assumed that: (1) 10% of participants will be lost to the

study by the end of treatment; an additional 15% of participants will drop out of treatment, resulting in 25% of participants randomized to placebo or 0.5mg DEX groups that would not complete treatment. We anticipate that 10% of completers will be lost to the study prior to the 3 month follow-up visits.

The effect size measure used,  $d$ , represents the standardized difference between sample means. Cohen (1988) has proposed that  $d = .30$ ,  $.50$ , and  $.80$  be categorized as “small,” “medium,” and “large,” respectively. We assume that a medium effect size—half a standard deviation—is the smallest clinically meaningful difference between DEX-augmented VRE vs. placebo-augmented VRE at the end of treatment.

For a two-group study design, 100 participants ( $n=50$  in each group) would be needed to achieve a minimum desired power of 85% to detect an effect size of  $.65$  with a 2-sided test at a significance level of 0.05.

Hypothesis 1: Patients who receive VRE+DEX will evidence more improvement on within-session measures (SUDs), on immediate post-treatment symptoms measures and on startle, SCR and HR, than the group who receives placebo.

To analyze pre-treatment and immediate post-treatment differences, the first analysis will compare the VRE+DEX condition to the VRE+placebo condition on the following outcome measures: 1) symptom measures (continuous variables); 2) psychophysiological measures (startle responses, cortisol levels, heart-rate, skin conductance) (continuous variables). It is expected that VRE+DEX participants will show significant improvement on all outcome measures immediately post-treatment compared to VRE+ placebo participants.

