Continuous variables will be analyzed using multivariate repeated measures ANCOVA with treatment condition being the between subjects factor, the pre-treatment vs. post-treatment condition being the within subjects factor, and the scale scores as the multiple measures accounting for appropriate covariates as determined through preliminary analyses discussed above. Adjusted means and mean differences as well as interaction terms will be obtained and evaluated. Categorical variables will be analyzed using logistic regression and controlling for appropriate covariates resulting in adjusted odd ratios.

An additional approach to testing this hypothesis will involve using two categorical measures of clinically significant improvement: 1) a 30% decrease in the CAPs, and 2) a rating of “much improved” or “very much improved” by the therapist and participant on the CGI inventory at the end of active treatment. These data will be analyzed using logistic regression with the inclusion of appropriate terms for the covariates and treatment-by-covariate interactions.

Furthermore, we will look at the number of sessions required to reach 70% improvement or maximum treatment response and the number of dropouts, predicting fewer sessions to reach 70% improvement or maximum treatment response and fewer dropouts in the VRE + DEX group.

Within-subject measures will also be obtained to assess improvement within sessions. SUDS and psychophysiological measures (heart rate and skin conductance) will be used to measure within session anxiety levels. Average and peak values of these continuous variables will also be analyzed using a repeated measures ANCOVA.

Hypothesis 2: Patients who receive VRE+DEX will evidence more improvement on follow-up assessments (symptom measures and psychophysiological responses) gathered 3, 6 and 12 months post-treatment compared to the patients who receive the placebo.

*Interval specific analyses:* First, the effectiveness of the VRE+DEX treatment will be analyzed for the two interval periods separately: from immediately post-treatment to the 3, 6 and 12 -month assessment. To test these time interval specific treatment effects, logistic regression will be used to compute adjusted odd ratios for dichotomous outcomes and multivariate

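### The responder model for Hypothesis 1 includes treatment-by-covariate interactions but does not say which DEX odds ratio is tested; if covariates are left uncentred, the treatment coefficient is the effect at covariate value zero

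*Combined protocol and SAP*

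**What the plan says.** All references are to the combined protocol and SAP.

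- **Section 10.2, Hypothesis 1, responder outcomes.** As an additional way of testing the hypothesis, the plan defines two binary outcomes at the end of treatment: a 30% CAPS reduction, and a CGI rating of much or very much improved. The model is given in one sentence: "These data will be analyzed using logistic regression with the inclusion of appropriate terms for the covariates and treatment-by-covariate interactions".
- **Section 10.2, Hypothesis 1, general rule.** Two sentences earlier, categorical outcomes are assigned to covariate-adjusted logistic regression that yields adjusted odds ratios. Interactions are not mentioned there.
- **Section 10.1, Group Equivalence.** Covariates are chosen from the data. A variable must differ between groups at P ≤ 0.15 and also be identified as a potential confounder; such variables "will be included as covariates in subsequent cross sectional and longitudinal analyses". Demographics and baseline values of key outcomes are among the candidates.
- **Section 10.2, Power and Sample Size.** The calculation is for a continuous outcome. "We set the Type I Error rate at 0.05 (two-tailed) for all computations". "For a two-group study design, 100 participants" (50 per group) "would be needed to achieve a minimum desired power of 85% to detect an effect size of" 0.65. No responder rate and no power for the responder outcomes are given.

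Sections 10.1 and 10.2 do not say whether covariates are centred, which coefficient or joint test decides the DEX effect on response, or whether a main-effects model is fitted first.

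**The concern.** Take one covariate x and treatment T (1 = DEX, 0 = placebo). The model is logit P(response) = b0 + b1·T + b2·x + b3·T·x. The DEX log odds ratio for a patient with covariate value x is b1 + b3·x. The coefficient b1, which standard software prints beside the treatment variable, is therefore the DEX effect at x = 0. For several candidate covariates no eligible patient can have that value: age runs from 21 to 65 (section 3.1), a 17-item PCL scored 1 to 5 totals 17 to 85, and a 20-item STAI-State scored 1 to 4 totals 20 to 80 (section 8.0).

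Two analysts could both follow the document and report different odds ratios and p-values. One would use the general sentence (main effects only), the other the responder sentence (interactions, raw scales). The second would be extrapolating outside the data, with a much larger standard error. These are the plan's only measures of clinically significant improvement under Hypothesis 1, so the choice should not be left until the data are seen.

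**Working it through.** **1. The plan's own figure.** For d = 0.65, two-sided alpha 0.05 and 85% power, n per group = 2(1.960 + 1.036)²/0.65² = 42.5, so 43 (44 with the t distribution). The plan assumes "10% of participants will be lost to the" study by the end of treatment: 2 × 44/0.9 = 97.8, so 98. N = 100 is reproduced. It leaves 50 × 0.9 = 45 measured per arm, with 86.2% power by the t distribution. This calculation does not involve the responder model.

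**2. Inputs for the responder outcomes.**
- From the plan: 45 per arm; two-sided alpha 0.05.
- Assumed, because the plan is silent: response 50% versus 75% (OR = 3, log OR = 1.099); covariate effect 0.5 log-odds per SD; no true interaction; one covariate with mean/SD = r, for r from 1 to 4.

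**3. Approximation.** In simulation the main-effects model gives a standard error of about 0.48 for the treatment coefficient. Adding an uncentred interaction multiplies it by about √(1 + r²). Approximate power is Φ(1.099/SE − 1.96) + Φ(−1.099/SE − 1.96).

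| r = mean/SD | √(1 + r²) | SE = 0.48·√(1 + r²) | 1.099/SE | Approx. power | Simulated power |
|---|---|---|---|---|---|
| no interaction | 1 | 0.48 | 2.29 | 63% | about 65% |
| 1 | 1.41 | 0.68 | 1.62 | 37% | about 41% |
| 2 | 2.24 | 1.07 | 1.02 | 18% | about 18% |
| 3 | 3.16 | 1.52 | 0.72 | 11% | about 11% |
| 4 | 4.12 | 1.98 | 0.56 | 9% | about 9% |

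With the covariate centred at its mean, the interaction model keeps about 66% power, the same as main effects only.

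**4. A second way of generating the data.** Dichotomise a normal outcome with d = 0.65, 50% placebo response (so 74.2% on DEX), and covariate-outcome correlation 0.3. At 45 per arm and r = 3, main effects only gives 68.6%, the centred interaction model 67.7%, and the uncentred treatment coefficient 11.1%. Across r = 0, 1, 2, 3, 4 and 5 the uncentred figure is 69%, 41%, 17%, 11%, 6% and 7%.

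**5. Is r between 1 and 4 realistic?** For a variable confined to [a, b], mean/SD is at least 2√(ab)/(b − a).
- Age 21 to 65: 2√1365/44 = 1.68, so SE inflation of at least 1.95.
- PCL 17 to 85: 2√1445/68 = 1.12, so at least 1.50.
- STAI-State 20 to 80: 2√1600/60 = 1.33, so at least 1.67.

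These are worst-case distributions. If values are spread uniformly over each range (an assumption), r is 3.4, 2.6 and 2.9, and simulated power is 10%, 13% and 10%.

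**6. Sensitivity.**
- *Baseline power* (d = 0.65, 45 per arm, by formula without covariates): 66.3% at 50% placebo response, and between 55.5% and 68.1% for placebo rates of 30% to 70%. At d = 0.5, the plan's smallest meaningful difference ("half a standard deviation"), it is 45.6%.
- *Completers.* The plan expects "an additional 15% of participants will drop out of treatment, resulting in 25% of participants randomized to placebo" or DEX not to complete treatment, leaving 50 × 0.75 = 37.5 per arm. Simulated with 38 per arm and r = 3: 61% for main effects, 9.5% uncentred.
- *Joint test of treatment plus interaction:* about 60% with one covariate and about 50% with three.
- *No average effect but a true interaction* (0.3 SD of outcome per SD of covariate): the uncentred coefficient rejects 14% of the time, against 5.5% for main effects.

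**The case against.** The strongest reply is that the plan does not prescribe the damaging analysis. The loss needs two things that it does not state: uncentred covariates, and a reader who tests the lone treatment coefficient. Centring only re-expresses the same fitted model, and with it power is about what main effects give. This stands, and it rules out three stronger readings that a reader might infer.

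- *That the interactions themselves destroy power.* They do not: 67.7% centred against 68.6% for main effects.
- *That the estimate could not be interpreted.* The DEX effect at the covariate mean, or averaged over patients, can be recovered from the same fit. What is missing is a statement of which one is reported.
- *That the trial's main test is compromised.* The responder analysis is described as additional. The continuous comparison comes first and carries the sample size, and the aims in section 2 are exploratory.

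Other points also stand. The screen in section 10.1 may admit no covariate, and then nothing changes. An admitted covariate may be categorical, in which case zero is a real patient group, though still only one subgroup. The wording does not clearly require an interaction for every covariate. Responder rates and covariate effects are assumptions.

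The general sentence on adjusted odds ratios does not settle the matter. It does not say that it governs the two responder outcomes, and the more specific sentence that follows gives those outcomes a different model.

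**Conclusion.** The concern holds as a gap in a stated model. For the responder outcomes the plan commits to a logistic model with treatment-by-covariate interactions and does not say which DEX effect is to be reported or tested. The default coefficient is the effect at covariate value zero, outside the possible range for several obvious candidates.

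The size depends on the reading. On the uncentred reading with one covariate, power drops from about 65% to between about 41% and 9% for mean/SD of 1 to 4, under the assumed 50% versus 75% response and 45 per arm. With a joint test it is about 50% to 60%. With centring, or with no qualifying covariate, the loss is negligible or nil.

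This should be fixed, but it does not threaten the trial: the continuous comparison and the N = 100 calculation stand as they are.

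**What to change.** Replace the responder-model sentence in section 10.2, Hypothesis 1, with:

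> *The DEX effect on each responder outcome is the odds ratio from a logistic model with treatment and the covariates as main effects only. Treatment-by-covariate interactions are fitted in separate exploratory moderator models with centred covariates.*

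This brings the responder analysis into line with the plan's general sentence on categorical outcomes. If the interaction model is to be kept as the main one, the minimum is to state that covariates are centred and which contrast or joint test decides the DEX effect; the joint test has the lower power shown above.

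The cost is a change of SAP wording and one extra model fit per outcome. No data collection or sample-size change is needed.

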#### **6.0 Therapy**

Treatment will commence following the pre-treatment assessment and all participants will be then randomized and seen for an introductory session and then treated once or twice per week for 6-11 therapy sessions, including one information gathering and preparation for VRE sessions. Patients will be randomized to receive dexamethasone or pill placebo before the VRE sessions. VRE will be limited to a minimum of 6 sessions and a maximum of 11 sessions, based upon reaching criterion of 70 % symptom improvement as indicated on the PTSD Symptom Scale or an agreement between clinician and participant that maximum treatment response has been achieved. All sessions will be individual and weekly or twice weekly. The first session will last approximately 90 minutes and will be spent in information gathering, treatment planning, and explaining the treatment rationale to the patient. Information gathering will review the history of PTSD and their military service and will include a brief psychosocial history, including review of prior treatment. The VRE sessions will last 90-minutes each. During VRE sessions patients will wear a head-mounted display with stereo earphones that will provide visual and audio cues consistent with Iraqi or Afghan military scenarios. The therapist will make appropriate comments and encourage continued exposure until anxiety has habituated. During exposure, information will be gathered on the participant's anxiety level through the use of a 0-100 SUDs scale. All therapists will have been trained in Prolonged Imaginal Exposure therapy (PE) followed by training in VRE by Drs. [name] and [name]. Drs. [name] and [name] will supervise all therapy.

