#### Measures at each Therapy Session

Expectancy of Therapeutic Outcome Questionnaire (ETOQ) assesses how logical the treatment appears, and the expectancy of success for the patient and for others. This measure is administered after session 1 only.

Clinical Global Impressions Scale, Severity of Illness (CGI-Severity; Guy & Bonato, 1970). This is a study personnel rated measure of severity of illness ranging from 0 (not assessed) to 7 (among the most extremely ill patients). This measure is administered after sessions 1–6.

Clinical Global Impression – Improvement (CGI-Improvement; Guy & Bonato, 1970). This is a study personnel rated measure of patient's improvement since start of study ranging from 1 (very much improved) to 7 (very much worse). This measure is administered after sessions 2-6.

Clinical Global Improvement Scale, Patient Report (CGI - Self Report; Guy & Bonato, 1970). This is a self-reported global measure of change in severity of symptoms, ranging from 1 (*very much improved*) to 4 (*unchanged*) to 7 (*very much worse*). This measure is administered after sessions 1-6.

The PTSD Symptom Scale is a 17-item interview used to aid in the detection and diagnosis of PTSD (described above), administered before sessions 2-6.

Subjective Units of Discomfort (SUDs) will be gathered during each exposure session (sessions 2-6). Participants will be asked to rate their level of discomfort on a scale of 0 (no anxiety) to 100 (panic levels of anxiety) every 5 minutes during the VR exposure.

Intent to Attend (Leon et al., 2007) is a short, two question survey asking participants how likely they are to complete all of the study and how likely they are to attend the next session.

Blinded Medication Check is a one-question measure to assess which medication the participant believes they took.

Cortisol Sampling will be obtained from saliva in order to measure post-dexamethasone cortisol levels and detect the presence of dexamethasone in saliva. Cortisol sampling methods are described below.

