### Interventions:

VRE. The VRE treatment program will consist of 90-minute individual treatment sessions. Procedures include education about common reactions to trauma, breathing retraining, prolonged (repeated) virtual exposure to trauma, and discussion of thoughts and feelings related to exposure exercises. The discussion addresses unrealistic beliefs about the self and the world, attempting to “process” material that came up during the exposure and make new associations explicit (e.g., “You see, by staying with the image long enough, your anxiety decreases.”) Session 1 is devoted to information gathering, education about common reactions to trauma, elaboration of the index trauma, breathing retraining, and fostering a therapeutic alliance. The remaining 5-10 sessions consist of VRE interventions and discussion of these experiences.

The patient will be encouraged to expose him or herself to traumatic memories triggered by the virtual environments, following guidelines for standard exposure therapy. As the number of sessions is limited, we are limiting exposure to the identified index trauma, and in some cases, a second traumatic event. The therapist asks the patient to give a SUDs (Subjective Units of Discomfort, 0= no anxiety and 100=maximum anxiety) rating approximately every five

minutes during all exposures as an indication of his level of anxiety. The therapist makes appropriate comments and encourages continued exposure until anxiety has decreased. The therapist simultaneously views on a video monitor all of the virtual environments in which patients are interacting and therefore is able to comment appropriately and is attempting to match stimuli that the patient is describing to the virtual stimuli, as much as possible, for example by landing the helicopter at the appropriate time in the memory, or by having gunfire, bombs, fog, or night time to match the memory. The 90-minute session will consist of 15 minutes of checking in with the patient about their functioning and anxiety since the last session, up to 45 minutes of exposure to their traumatic memories and the virtual stimuli, followed by processing and discussion about the material from the exposure. Information is gathered each session on any other exposure the patient may have conducted, although no homework will be assigned, as patients will only be on study medication for office visits.

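### If exposures end when anxiety has fallen, average SUDs says little about how fast it fell, and peak SUDs says little in any case; the plan has no within-session measure of speed.

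*Combined protocol and SAP*

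**What the plan says.** Section 6.0 (Therapy) has the therapist "encourage continued exposure until anxiety has habituated". The Interventions text in section 8.0 puts it as "encourages continued exposure until anxiety has decreased" and allows "up to 45 minutes of exposure to their traumatic memories and the virtual stimuli", which is a ceiling and not a fixed length. Neither place gives a numerical criterion for habituation.

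Under Measures at each Therapy Session, SUDs are collected in sessions 2-6, "every 5 minutes during the VR exposure", on a 0-100 scale.

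Hypothesis 1 in section 10.2 lists SUDs as the within-session outcome. The analysis text gives the purpose, "Within-subject measures will also be obtained to assess improvement within sessions", and then the summaries: "Average and peak values of these continuous variables will also be analyzed using a repeated measures ANCOVA". It defines no common time window, slope, end-of-exposure value or time to habituation. The one speed outcome in the plan counts sessions to 70% improvement or maximum response. That is a between-session measure and does not use SUDs.

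**The concern.** If exposure continues until anxiety has come down, the number of ratings depends on the response being compared. A patient who settles quickly gives few ratings. A patient who settles slowly gives more, including the late low ones. When both start and finish at similar levels, their averages are similar whatever the speed.

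The Objectives frame Hypothesis 1 as DEX facilitating fear extinction, and faster decline within a session is one direct way for that to show. With average and peak as the only summaries, the trial could miss such an effect although the ratings needed to see it are on file.

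**Working it through.** **Plan's own figure.** Section 10.2 gives 100 participants (50 per arm) for at least 85% power at d = 0.65, two-sided 0.05. By the normal approximation, power is Φ(0.65·√(n/2) − 1.96). For n = 50 this is Φ(3.25 − 1.96) = 90.2%. For n = 45, after the stated 10% loss, it is Φ(3.08 − 1.96) = 86.9%. The figure is reproduced, but it refers to the post-treatment comparison. The plan states no power for SUDs.

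**Inputs from the documents.** Ratings every 5 minutes; ceiling 45 minutes, so at most 10 ratings (0 to 45); sessions 2-6, so five sessions; 45 per arm.

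**Assumed, not in the documents.** All SUDs levels, rates, variances and the stopping level.

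**Step 1: two straight-line paths, both inside 45 minutes.**
- Steps of 5: 80, 75, …, 40. Nine ratings over 40 minutes; mean (80 + 40)/2 = 60; peak 80.
- Steps of 8: 80, 72, 64, 56, 48, 40. Six ratings over 25 minutes; mean 360/6 = 60; peak 80.

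The second path is 8/5 = 1.6 times as fast, yet both summaries agree. Over the first six ratings of each path the means are 405/6 = 67.5 and 60.

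**Step 2: exponential decline.** For S(t) = P·exp(−kt) stopped at cP, the average over the window is P(1 − c)/(−ln c). The rate k cancels. With P = 80 and c = 0.5 this is 40/0.693 = 57.7. With 5-minute ratings, half-lives of 10, 20, 30 and 40 minutes give averages of 58.9, 58.3, 58.1 and 58.0. Over a fixed 45 minutes they would be 26.5, 41.4, 50.2 and 55.9.

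**Step 3: simulated power.** Assumed: start 75 (SD 12), placebo fall of 4-6 points per 5 minutes (SD 1.5), rating noise SD 5, DEX falls 1.4 times as fast, five sessions, 45 per arm. Ranges run over the placebo falls.

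| Summary | Exposure rule | Power |
|---|---|---|
| Average | stop at half of start, or 45 min | 10-34% |
| Average | stop at 30% of start, or 45 min | 49-63% |
| Average | always 45 min | 74-95% |
| Peak | stop at half, or always 45 min | 5-8% |
| First minus last | stop at half, or 45 min | 50-97% |
| Ratings to threshold, or slope | stop at half, or 45 min | 96-100% |

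In the stop-at-half runs the ceiling leaves 13-51% of placebo sessions short of the threshold. That is why first-minus-last keeps much of its power.

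**Step 4: a different model.** Exponential curves, one session, 50 per arm, two-group t-test, stop at half of peak. Half-lives of 20 against 10 minutes give 16% power for the average, 5% for peak and about 100% for time to habituation. At 60 against 30 minutes, 72% of placebo sessions reach the ceiling and the average has 75%. At 80 against 40, 92% reach it and the average has 92%.

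**Step 5: a lower starting level and no change in speed.** An 8-point lower start gives 80-85% power for average and peak.

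**The case against.** The strongest reply is that no passage says exposure ends at habituation. The therapist encourages continuation, no threshold is given, a mere decrease fits almost any end level, and a second trauma may be worked on. Exposures may well fill the 45 minutes, and the average then has reasonable power. This stands as a limit on size. The wording still makes a variable length the plainer reading, and how well the average performs should not hang on how often the ceiling is reached.

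A second reply is that SUDs are there to measure anxiety level. The Significance section expects DEX to reduce fear before the session starts, and average and peak are suited to that. This also stands, and it is why both should be kept.

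A reader might infer more than the documents support:
- **That a start-to-end change fails in the same way.** This is exact only when both arms reach the same end level before the ceiling. Otherwise the loss is partial (50-97% power).
- **That the variable window is what blunts peak.** Peak has 5-8% power even when every exposure runs 45 minutes, because it occurs early. A common window would not rescue it.
- **That a null SUDs result could not be interpreted.** It would still be evidence against a sizeable reduction in fear level. It would say little about speed.

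**Conclusion.** The concern holds in a limited form. Where most sessions end at habituation before 45 minutes, average SUDs is largely insensitive to the speed of decline. Peak is insensitive to speed under either reading of the exposure rule. The plan contains no within-session summary that would show speed directly.

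The cancellation in the average is exact arithmetic for paths sharing a start and an end level. The power figures rest on assumed SUDs curves and above all on the assumed stopping level, so they show the direction and possible size of the loss and do not forecast it. They cover SUDs only; heart rate and skin conductance get the same two summaries but were not modelled.

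The scope is the within-session part of Hypothesis 1. The post-treatment comparison that sets the sample size is untouched.

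**What to change.** In section 10.2, keep average and peak, labelled as measures of anxiety level, and add one prespecified within-session speed outcome from the ratings already collected:

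- the rate of SUDs decline, as a mixed-model slope over minutes of exposure, compared by arm; or
- minutes to the first rating at or below a prespecified fraction of that session's initial SUDs, censored at the end of exposure.

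Also compute the average over a common initial set of ratings for every patient and session.

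The cost is SAP wording and some derivation work, with no new data and no change to the exposure rule. There are two drawbacks. A session may end once anxiety has eased but before the threshold is met, so fast decliners could be censored early and the censoring may be informative. For that reason the slope should be the main analysis or at least a sensitivity analysis. The common set of ratings can be no longer than the shortest sessions allow.
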